11.1.3 Methods for Evaluation of Measurable Disease

Pancreas protocol CT scans (biphasic imaging, 1.25 mm cuts) and/or FDG PET-CT scans (optional and if recommended by the treating physician) will be obtained at all follow-up intervals as described in the treatment calendar.

11.1.4 Response Criteria

11.1.4.1Evaluation of Target Lesions

Patients' responses to therapy will also be evaluated clinically after completion of their Linac based SBRT. The following are clinical definitions for response:

CR = complete alleviation of pain or other symptoms thought to be related to the index lesion

PR = improvement, but not complete elimination, of pain or other symptoms thought to be related to the index lesion

PD = worsening of pain or other symptoms thought to be related to the index lesion SD = does not meet criteria for PR or PD

Radiographic response will be defined as outlined in section 11.1.2.

11.1.4.2Evaluation of Non-Target Lesions

Standard radiographic criteria will be utilized for non-target lesions. Any disease outside of the pancreas or periampullary region will be considered metastatic disease. If possible a biopsy should be obtained to confirm metastasis.

11.1.4. 3Evaluation of Best Overall Response

This will be based upon the response of the treated lesion as described above.

11.1.5 Duration of Response

The criteria for overall response will be the time between treatment and first sign of local progression or development of new metastatic disease.

11.1.6 Progression-Free Survival (or other parameters)

The criteria for time to progression and progression-free survival (PFS) will be the duration from Linac based SBRT treatment to documented local/regional or distant progression or death. Local PFS will be measured as the duration from Linac based SBRT treatment to local progression or death from any cause.

11.1.7 Response Review

All responses will be reviewed independently by a board certified radiologist at the study's completion. Each image will be reviewed by the PI. Simultaneous review of the patient's chart will also occur at this time. PET/CT images (if available as per the recommendation of the treating physician) and PERCIST measurements will be made by [name] and a staff member in the nuclear medicine department.

12. DATA REPORTING / REGULATORY CONSIDERATIONS

12.1 Monitoring Plan

Johns Hopkins University will conduct yearly study audits to review subjects' timely and complete enrollment, registration into the electronic database, and follow-up per study calendar. More frequent monitoring will take place as needed. Trial monitoring with subject chart and trial binder reviews will be done by Johns Hopkins University per Sidney Kimmel Cancer Center guidelines.

Subject data will be documented and stored in the electronic database Oncospace & Mosaiq, the software and infrastructure being supplied by JHH.

12.1.1 Data Management

This is a DSMP Level I study under the SKCCC Data Safety Monitoring Plan (9/22/2011). The Clinical Research Office QA Group will perform an audit after the first subject has been treated and then periodically depending on the rate of accrual and prior audit results. All trial monitoring and reporting will be reviewed annually by the SKCCC Safety Monitoring Committee. The PI is responsible for monitoring the study. Data must be reviewed to assure the validity of data, as well as, the safety of the subjects. The PI will also monitor the progress of the trial, review safety

reports, and clinical trial efficacy endpoints and to confirm that the safety outcomes favor continuation of the study.

12.1.2 Data Entry and Compilation

Research Staff (Coordinators, Nurse, or Co-Investigators) will enter/scan subject data into Oncospace, which will include:

- Eligibility or Inclusion/Exclusion Criteria
- Patient Demographics
- Pre-Study Evaluation including H & P, Allergies, and Review of Systems
- Surgical Procedures, with dates and findings (including EUS, biopsy (if needed), seed placement, and/or stent (if recommended)
- Scan dates (PET/CT (if available) and/or CT)
- Treatment planning date
- Pre-Study Labs including hematology, chemistry, and tumor markers (CBC, CMP and CA 19-9)
- Radiation therapy dates and toxicities reported
- Follow-up Evaluations including H&P, Review of Systems, and toxicities
- Follow-up labs and dates
- Completion of QOL questionnaires
- Subject study withdrawal, date, and reason
- Concomitant medications, specifically PPIs and antiemetics, prescribed per protocol and if reportedly taken by subject

Information will be entered from source documents or from Case Report Forms which are formatted to capture data as it will be entered into the database. If information is entered from source documents directly into Oncospace, Case Report Forms can be printed out and signed or signed electronically.

The PI will be responsible for maintaining the clinical protocol and subjects' study charts, reporting adverse events, assuring that consent is obtained and documented, and reporting the status of the trial in continuing renewals submitted to their IRB and trail monitoring group(s) as per JHH protocol.

There will be password-protected limited access to the database in order to maintain privacy (See Confidentiality below).

12.2 Stopping Rules

All outcome data (toxicity and efficacy) will be reviewed every 6 months by the Principal Investigator and key Co-Investigators. This study will be monitored by the JHH IRB. All potential adverse events will be reported to the SKCCC Data Safety Monitoring Committee and the JHH IRB. An interim analysis is planned to assess late grade 2 or greater gastritis, enteritis, fistula, ulcer, or late grade 3 or greater GI toxicity when 16 patients are accrued. If 7 or more patients have late grade 2 or greater gastritis, enteritis, fistula, ulcer, or late grade 2 or greater gastritis, enteritis, fistula, ulcer, or late grade 2 or greater gastritis, enteritis, fistula, ulcer, or late grade 3 or greater GI toxicity within one year, the trial will be halted (note: accrual will continue while interim analysis is being conducted). After the first 16 patients are followed up for one year, we will also estimate the 1-year local progression free survival. If the upper bound of a two-sided 98% confidence interval (alpha = 0.02) of local progression free survival is below 30% in cohort A, or less than 50% in cohort B, the accrual at that cohort will be halted for lack of efficacy.

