13.4.2 Sample Size Justification

The primary goal of this study is to access the late gastrointestinal toxicity rates including grade 2 or greater gastritis, fistula, or ulcer and any other grade 3 or greater gastrointestinal toxicity in Linac based SBRT patients. Two cohorts will be accrued in this study; one will be patients who recurrent or residual disease after previous chemoradiation therapy (Cohort A), and the other will be patients who had recurrent or residual disease after surgery and/or chemotherapy without radiation (Cohort B). Cohort A will be treated with 5 Gy x 5 for palliative retreatment, and Cohort B will be given 6.6 Gy x 5 for definitive treatment. Two cohorts will be evaluated separately.

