The sample size is 60 patients per cohort. The primary outcome used to determine the sample size is the percentage of individuals with a late gastrointestinal toxicity (grade 2-4) at one year. The late grade 2 or greater toxicity rates was previously observed for other treatment regiments for locally advanced pancreatic cancer were approximately 40%. We hypothesize that in each cohort, the toxicity rate for this regimen will be 20%, a 50% reduction. The stopping rules for futility were calculated based upon a two-stage design with a total sample size of 60 and an interim analysis of 16 patients (note: accrual will continue while interim analysis is being conducted). Within 16 patients, if 7 or more patients have late grade 2 or greater gastritis, enteritis, fistula, ulcer, or late grade 3 or greater GI toxicity, the trial will be stopped. If 6 or fewer patients have late grade 2 or greater gastritis, enteritis, fistula, ulcer, or late grade 3 or greater GI toxicity, then the study will continue enrolling patients until 60 patients have been accrued. After 60 patients are enrolled, if 17 or more of the patients have late grade 2 or greater gastritis, enteritis, fistula, ulcer, or late grade 3 or greater GI toxicity, the null hypothesis will not be rejected. If 16 or fewer of the patients have late grade 2 or greater gastritis, enteritis, fistula, ulcer, or late grade 3 or greater GI toxicity, we will conclude that one year late toxicity is below 40%. This design will reach 91% power with 2% type I error for grade 2 or greater late toxicity, and the probability of early termination is 0.47. In addition, this sample size will reach 89% and 90% power to test the increase of 1-year local progression free survival from 30% to 45% in cohort A and 50% to 65% in cohort B, respectively.

The calculation is based on a one-sided test at significance level 0.04, assuming exponential distribution for local progression time and 2.5 year uniform accrual time with 1 year follow up.

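### The late-toxicity interim does not say how long the first 16 patients are followed: taken literally it would almost never stop a cohort, and run at one year it acts when about 40 of 60 are enrolled

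*Combined protocol and SAP*

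**What the plan says.** Section 12.2 (Stopping Rules) plans an interim look at the primary endpoint, including "late grade 3 or greater GI toxicity when 16 patients are accrued". The rule fires at 7 or more patients with qualifying "GI toxicity within one year, the trial will be halted (note: accrual will continue while interim analysis is being conducted").

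Section 13.4.2 (Sample Size Justification) repeats the boundary: "Within 16 patients, if 7 or more patients have late grade 2 or greater gastritis" or another qualifying event, the trial stops. It gives 91% power, 2% type I error and a 0.47 probability of early termination. With 16 or fewer events in 60, "we will conclude that one year late toxicity is below 40"%. Neither section states a follow-up time for the 16 patients.

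The neighbouring look at local progression-free survival does state one: "After the first 16 patients are followed up for one year, we will also estimate the 1-year local progression free survival".

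The unit also differs. The toxicity rule in 12.2 halts the trial. The efficacy rule in the same section says "the accrual at that cohort will be halted for lack of efficacy", and 13.4.2 says "Two cohorts will be evaluated separately".

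**The concern.** An event is late only after 3 months, and the design counts events up to one year. At the 16th accrual no patient has one-year data and many are not yet past month 3. A team that ran the look on that date would be following the text, yet would see almost none of the events on which the 0.47 depends. A team that waited a year would also be following a fair reading, and could reach the opposite decision.

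This is the only numeric boundary for late toxicity before the final analysis. Outcome data "will be reviewed every 6 months by the Principal Investigator and key Co-Investigators", a safety committee reviews the study annually (12.1.2), and the study may be stopped on recommendation (13.3). Any of these could act sooner, but no text ties the 7-event count to them.

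Two details are also missing: whether the halt applies to a cohort or to the whole trial, and how patients who die or withdraw before 12 months count among the 16.

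**Working it through.** **Inputs.** Boundary 7 of 16, final boundary 16 of 60, rates 40% and 20%, 60 per cohort (13.4.2). Accrual of 2 to 3 per month per cohort (13.4.1); 60 patients in 30 months (6.3, 13.4.2) is 2 per month. Late means after month 3 (7.1, 13.1.1). Assumptions: even accrual, SBRT at accrual, and 40% read as a crude proportion of treated patients. The timing of events within months 3 to 12 is assumed, so a range is shown.

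**1. The plan's own figures.** Early termination is P(X ≥ 7 | n = 16). Success is the sum over x ≤ 6 of P(X₁ = x | 16) × P(X₂ ≤ 16 − x | 44).
- At 40%: early termination 0.473, type I error 0.021.
- At 20%: early termination 0.027, power 0.908.

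All three stated figures reproduce, given complete one-year outcomes on all 16. With no first stage the final test gives 0.022 and 0.923, so the interim hardly affects it.

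**2. Literal look at the 16th accrual.** Patient i has (16 − i)/rate months of follow-up.
- At 2 per month the longest is 15/2 = 7.5 months, and 9 patients are past month 3 (10 counting the one exactly at month 3).
- At 3 per month the longest is 15/3 = 5 months, and 6 to 7 are past month 3.

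With uniform timing, each patient followed f > 3 months has event probability 0.40 × (f − 3)/9. At 2 per month the values of f − 3 sum to 22.5, so 0.40 × 22.5/9 = 1.0 event is expected. The exact probability of 7 or more is:

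| Event timing (true rate 40%) | 2 per month | 3 per month |
|---|---|---|
| Uniform, months 3–12 | 0.0000027 | 0 |
| All within months 3–6 | 0.0021 | 0 |
| All at month 3 (extreme) | 0.025–0.055 | 0–0.0016 |

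The plan states 0.47. If the 16 were pooled over both cohorts at 4 per month combined, only 4 patients would have reached 3 months, and 7 events would be impossible.

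**3. One-year look.** Enrolled at the decision = 16 + 12 × rate: 16 + 24 = 40 at 2 per month, 16 + 36 = 52 at 3 per month. Expected enrolment at a 40% rate:
- 2 per month: 0.473 × 40 + 0.527 × 60 = 50.5
- 3 per month: 0.473 × 52 + 0.527 × 60 = 56.2
- accrual paused at 16: 0.473 × 16 + 0.527 × 60 = 39.2

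**4. Halting at the 7th event.** Simulation (200,000 runs, 40% rate, uniform timing) gives mean enrolment in stopped cohorts of 29.7 at 2 per month and 39.3 at 3 per month.

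| Rule | Expected enrolment, 2 (3) per month | Saved against one-year look |
|---|---|---|
| Halt at 7th event, known at once | 45.7 (50.2) | 4.9 (6.0) |
| Halt at 7th event, found at 4-, 6-, 9- and 12-month visits | 47.2 (52.4) | 3.3 (3.8) |

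Other timings, with events known at once, save 8.5 (11.9) if all fall in months 3–6 and 3.9 (4.9) if all fall in months 6–12. If the 6-monthly reviews already applied the count, expected enrolment would be 48.5 (54.3), and the further saving 2.8 (4.1), or 1.8 (3.3) if visit-detected.

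**5. Early deaths.** The protocol cites 12-month survival of 21% (3.3) and 50% (3.2). That gives 16 × 0.79 = 12.6 and 16 × 0.50 = 8 deaths before 12 months. Suppose 40% is instead the risk in the absence of death, survival is independent and exponential with median 7 to 11.4 months (3.3, 3.2), and deaths count as non-events. The crude rate is then about 20–30%. Early stopping falls to 0.02–0.09 (uniform timing) or 0.09–0.19 (months 3–6), and the final test declares success about 30–92% of the time.

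**The case against.** The best reply is that the plan means a one-year look. The boundary counts events over one year, the final conclusion is about one-year toxicity, the efficacy look on the same 16 is introduced with *also*, and 0.47 reproduces only with complete outcomes. The accrual trigger may identify which patients are counted, not the date of the count. Both sections disclose that accrual continues, so enrolment beyond 16 is a stated choice. The planned pace is 2 per month, so 40 is the main figure and 52 the fast case. The saving is a few patients, and other safety reviews exist.

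Most of this stands. A reader might infer that the stated operating characteristics are wrong, that the final test is compromised, or that over-enrolment is hidden. The documents support none of these: the figures reproduce, the final test barely moves on the crude-proportion reading, and continued accrual is written down. A reader might also infer that the rule would wait indefinitely on patients who have died; no text says so. The 21% survival figure comes from a single-fraction series that included 19% metastatic patients, whom this trial excludes, so 13 deaths in 16 may be high.

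The unit question is partly answered by 13.4.2, which sizes and evaluates each cohort separately. Only the wording of 12.2 conflicts.

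What remains is that the text gives an accrual trigger and no follow-up time, and that followed as written the rule fails. The size of enrolment at a one-year decision is also not given beside the 0.47.

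**Conclusion.** The point holds as an unstated follow-up time that makes the rule ambiguous. On the literal reading, a cohort with a true 40% rate would pass the look almost every time under each event timing tried. On the likelier one-year reading, the rule performs as stated, but at the decision two thirds of the cohort (40/60), or 87% at 3 per month (52/60), is already enrolled.

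What is lost is early stopping. The gain from a rule that acts at the 7th event is modest: on average 5 to 6 patients per cohort at a true 40% rate under uniform timing, 3 to 4 if events are found only at visits, and fewer if the 6-monthly reviews already use the count. At a true 20% rate the boundary fires in only 2.7% of cohorts.

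The 0.47, 2% and 91% hold only if 40% and 20% are crude proportions of all treated patients. How early deaths and withdrawals are counted is therefore a substantive choice, which the plan does not make.

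**What to change.** In 12.2 and 13.4.2, state:

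> In each cohort, accrual halts as soon as a 7th patient among the first 16 treated has a qualifying late event within one year of SBRT. Otherwise the stage-1 decision is made once each of the 16 has had a qualifying event, completed 12 months of follow-up, died or withdrawn.

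Beside the 0.47, add:

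> This assumes complete one-year outcomes on all 16. About 40 of 60 patients (52 at 3 per month) are expected to be enrolled when the 16th reaches 12 months.

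The sponsor should also:
- reconcile the halt of the trial in 12.2 with the separate evaluation of cohorts in 13.4.2, and confirm that the unit is the cohort, because the wording above assumes it;
- choose and state how deaths and withdrawals before 12 months count, say whether 40% and 20% are crude proportions, and report the number of such patients with the event count.

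**Cost.** The decision is still 7 or more of 16, so sample size and (on the crude-proportion reading) error rates do not change. Accrual does not pause unless the 7th event occurs. The change does need a running count per cohort with prompt attribution to SBRT. It also needs capture of grade 2 gastritis, enteritis, fistula and ulcer: the addendum in 7.2 keeps toxicity below grade 3 off the Master AE Log and Case Report Forms, so a form item or a defined chart extraction is required.

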12.3 Confidentiality

Study data will be maintained in password protected computer files. Only research personnel listed on this protocol will have access to this information. Only the patients unique IDN will be used. The patient's name or other public identifiers will not be included in any information shared with other investigators. The study data with identifiers will be kept at Johns Hopkins under a separate confidential file.

13. STATISTICAL CONSIDERATIONS

13.1 Endpoints

13.1.1 Primary Endpoint

To evaluate late (>3 months after Linac based SBRT) grade 2 or greater gastritis, fistula, enteritis, or ulcer, or any other grade 3 or greater gastrointestinal toxicity attributable to fractionated Linac based SBRT.

- 13.1.2 Secondary Endpoints
 - To determine rates of local progression free survival, overall survival, metastasis-free survival, and progression-free survival at 3, 6, and 12 months from Linac based SBRT.
 - To evaluate acute toxicity, defined as any grade 3 or greater gastrointestinal toxicity within 3 months of treatment.
 - To use FDG-(if available as per the recommendation by your treating physician) /CT scans for assessment of tumor response and progression.
 - To evaluate the role of FDG-PET scans in treatment planning.
 - To assess the quality of life before and after fractionated Linac based SBRT.
 - To further standardize Linac based SBRT delivery and dosimetric parameters.
 - To compare toxicity and outcomes among patients treated with fractionated Linac based SBRT delivered as 5 Gy x 5 (Cohort A of current protocol), 6.6 Gy X 5 (Cohort B of current protocol), 25 Gy X 1 (previous study), and 5-10 Gy x 3 (previous study).
 - To evaluate pain control (as define by pain medication requirements at 3, 6, and 12 months following Linac based SBRT.

13.2 Analysis Populations

Efficacy analysis will be conducted on all patients who complete Linac based SBRT.

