We recently presented the preliminary results of our phase II multi-center trial of gemcitabine (GEM) and fractionated Linac based SBRT to determine if a high rate of LPFS with reduced toxicity could be achieved. After multidisciplinary review, 32 pts with locally advanced PDA received GEM in sequence with Linac based SBRT (6.6 Gy in 5 consecutive daily fractions, 33 Gy total). LPFS, metastasis free survival (MFS), and overall survival (OS) were measured from date of tissue diagnosis. Objective tumor response (OTR) was assessed by RECIST/PERCIST. EORTC QLQ-C30/PAN26 questionnaires were used to measure QOL. Median f-up was 12 mos (range, 2-23). Mean age was 69.9 yrs (SD, 9.8) and 62% were male. Patients received a mean of 2.2 (SD, 1.0) GEM doses prior to SBRT and 8.3 (SD, 5.6) doses total. All pts completed SBRT. Median OS was 15.9 months (95% CI, 12.7-18.8). Stratification by CA19-9 > or < 90 at diagnosis yielded a hazard ratio of 6.2 for > 90(p=0.021). Median LPFS has not been reached and median MFS was 10.2 mos (95% CI, 2.9-17.5). LPFS rate at 1 year was 87%. OTR on CT was seen in 41%, while 41% had stable disease and 18% progressed. Tumor metabolic activity decreased in 17/18 patients with pre/post- Linac based SBRT PET available. Mean peak SUV was 4.0 pre- Linac based SBRT versus 2.4 post-Linac based SBRT (p=0.002). Median CA19-9 was reduced from 124.7 prior to SBRT to 43.9 afterwards. Acute toxicity included: grade 2 anorexia (37%), fatigue (28%), nausea (22%), abd pain (19%), weight loss (9%), diarrhea (3%); gr 3 nausea (9%); and gr 4 nausea (6%). Late gr \geq 3 GI toxicity was seen in 9%. Mean QOL score 4 wks post-Linac based SBRT was similar to baseline (p=0.38). At 6 most here was a trend towards improved QOL (p=0.07). Overall, fractionated Linac based SBRT with GEM achieved high rates of LPFS and tumor response. Minimal grade ≥ 3 acute and late toxicity was observed. Linac based SBRT is more likely to benefit patients with Ca-19-9 <90. A combination of Linac based SBRT with more aggressive chemotherapy may further improve outcomes.

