6.1.4 Linac based SBRT Treatment Delivery

Patients will receive 5 fractions of 5 Gy or 6.6 Gy delivered over a five-day period, as delineated above, based on whether or not they have received prior radiation therapy to the pancreatic region. Ideally all 5 fractions should be delivered Monday through Friday; however, treatment may be delivered over 2 weeks, as long as the patient receives at least 2 fractions per week.

Treatment Delivery (LINAC-based):

- 1) Initial patient positioning will be based on volumetric kV (cone-beam CT) imaging with shifts to bony anatomy as appropriate.
- 2) Orthogonal kV/MV or kV/kV projection imaging will be used to verify the location of the fiducials prior to delivery of first treatment beam. A secondary shift based on the location of fiducials may be utilized, as indicated by the position of the fiducials. For free-breathing treatments, kV fluoroscopic images should be obtained to confirm the anticipated position of these fiducials during the entire respiratory cycle.
- Active monitoring of treatment delivery accuracy will be accomplished using kV and/or MV projection imaging, either immediately before or during all (or a subset of) treatment fields.

- 4) Patient-specific dosimetric quality assurance (QA) will be performed as per standard practice in the Department of Radiation Oncology and Molecular Radiation Sciences at Johns Hopkins Hospital.
- 6.1.5 Post-Linac based SBRT Follow-Up Following Linac based SBRT, all patients will be monitored clinically and with serial imaging (CT scans and/or PET/CT if possible and as deemed necessary by the treating physician).

A detailed medical history with physical examination and quality of life assessment will be performed at 4-6 weeks, 4 months, 6 months, 9 months and 1 year after radiation treatment.

In years 2-5, the follow up interval will be every 3-6 months, as determined by the principal investigator. Follow up intervals may also be more frequent as indicated clinically. A complete blood count (CBC) with differential, comprehensive chemistry panel, tumor marker studies, and quality of life assessment will be performed at each follow-up interval.

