13.6 Data Analysis

We will perform separate analyses for Cohorts A and B. Descriptive summary statistics (mean, median, standard deviation, range, or proportion) will be presented for demographic and clinical characteristics of patients or treated lesions.

Toxicity will be summarized by type and grade for each cohort. The rate of grade 3 or higher GI toxicity will be estimated along with its 95% CI. This study will evaluate the efficacy of fractionated Linac based SBRT based on local-regional progression free survival (LFSP). LPFS is defined as the elapsed time from the start date of Linac based SBRT treatment to the date of documented local/regional tumor progression or death, whichever occurs first. We will plot the Kaplan-Meier curve for LPFS and estimate 1-yr local control and its 95% confidence interval based on KM estimate and Greenwood's formula. In addition, we will consider death without local progression as a competing event, and estimate cumulative incidence rate of local-regional progression using a competing risk analysis.

Other outcomes to be studied in this group of patients include, overall survival (OS), progression free survival (PFS) and quality of life. OS is defined as the elapsed time from the start date of Linac based SBRT treatment to death due to any cause; PFS is the time from the start date of Linac based SBRT treatment to disease progression or death, whichever occurs first. OS and PFS will be summarized using Kaplan-Meier plot.

Quality of life will be assessed via EORTC QLQ-C30 (v3.0) questionnaires. Our study population is pancreatic cancer subjects, and the analysis will be focused on Global Health Status/QoL scale, symptom scale (fatigue, pain), and functional scale (physical functioning, role functioning, emotional functioning). For each module, summary statistics of the score will be reported as baseline and follow up time. Changes of quality of life score before and after treatment will be tested via paired t-test. In addition, mixture effect models will be fitted for accessing the quality of life changes over time. The frequency of patients who reach minimal clinically important difference of 10-points change from baseline will be tabulated by time. The time to definitive deterioration in quality of life will be analyzed using the Kaplan Meier method.

REFERENCES

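### Efficacy is analysed only in patients who complete SBRT although the clock starts at the first fraction, so LPFS would be biased upward if some patients stop early and do worse

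*Combined protocol and SAP*

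**What the plan says.** Section 13.2 is a single sentence and defines a single population: "Efficacy analysis will be conducted on all patients who complete Linac based SBRT". It does not define completion; I read it as all five fractions.

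Section 13.6 makes LPFS the efficacy measure ("This study will evaluate the efficacy of fractionated Linac based SBRT based on local-regional progression free survival") and sets its origin: "LPFS is defined as the elapsed time from the start date of Linac based SBRT treatment". Death counts as an event. PFS and OS have the same origin.

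On the length of treatment, section 6.1.4 says "Patients will receive 5 fractions of 5 Gy or 6.6 Gy delivered over a five-day period" but adds that "treatment may be delivered over 2 weeks, as long as the patient receives at least 2 fractions per week".

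Section 13.4.2 bases the LPFS power on the full cohort ("The sample size is 60 patients per cohort"), testing an increase in "1-year local progression free survival from 30% to 45% in cohort A" and from 50% to 65% in cohort B, one-sided at 0.04. It makes no allowance for non-completion.

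The only completion figure for the five-fraction 6.6 Gy schedule is in section 3.3, for 32 patients with locally advanced disease: "All pts completed SBRT".

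No section gives an all-treated analysis, a sensitivity analysis or a landmark at completion, or says how a patient who stops part-way is counted.

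**The concern.** Entry to the analysis depends on something that happens after the clock has started. A patient who dies, deteriorates or stops for toxicity between the first and last fraction is at risk under section 13.6 but removed by section 13.2, and that patient's later outcome goes too. If such patients do worse than completers, which is the natural expectation, the completers' LPFS overstates the LPFS of everyone who started.

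There is no control arm in which the same selection could cancel. LPFS is compared with fixed rates of 30% and 50%, so any upward shift moves the result towards success. The same endpoint drives the lack-of-efficacy stop after 16 patients (sections 12.2 and 13.5). If section 13.2 also governs that interim look, leaving out early failures makes the stop less likely to be triggered.

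**Working it through.** **Inputs.** From section 13.4.2: n = 60 per cohort; one-year LPFS 30% vs 45% (A) and 50% vs 65% (B); one-sided α = 0.04; exponential times; 2.5 years' uniform accrual plus 1 year of follow-up. From section 3.3: 32 of 32 completed. Not in the documents, so assumed and varied: the share f of starters who do not complete, and their one-year LPFS, s.

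**Step 1: reproduce the stated power.** With λ = −ln(one-year LPFS), expected events are d = n[1 − (e^(−λ) − e^(−3.5λ))/(2.5λ)], and

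power = Φ{[ln(λ0/λ1) − z(0.96)/√d0]·√d1}, with z(0.96) = 1.751.

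- A: λ0 = 1.204, λ1 = 0.799, d0 = 54.3, d1 = 48.3. Power = Φ{(0.411 − 0.238) × 6.95} = 88.6% (stated 89%).
- B: λ0 = 0.693, λ1 = 0.431, d0 = 45.7, d1 = 36.1. Power = Φ{(0.476 − 0.259) × 6.01} = 90.4% (stated 90%).

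Both agree, so the same test model is used below.

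**Step 2: LPFS among completers.** If LPFS among all starters is S, completers show (S − f·s)/(1 − f). At f = 5%:

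- A, all non-completers fail (s = 0): 0.30/0.95 = 31.6%. Half the average (s = 0.15): (0.30 − 0.0075)/0.95 = 30.8%.
- B, s = 0: 0.50/0.95 = 52.6%. Half the average (s = 0.25): (0.50 − 0.0125)/0.95 = 51.3%.
- If s = S, the shift is zero in both cohorts.

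**Step 3: chance of rejecting when the LPFS of all starters equals the null.** Put the completers' LPFS into the step 1 formula in place of the alternative, treat it as exponential, and use 60(1 − f) patients, rounded. Example, A, f = 5%, s = 0: d0 = 51.6, d1 = 51.1, ln(1.204/1.153) = 0.0435, giving Φ{(0.0435 − 0.2437) × 7.15} = 0.076.

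| Non-completion f | A: half average to all fail | B: half average to all fail |
|---|---|---|
| 0% | 4.0% | 4.0% |
| 2% | 4.6–5.2% | 5.0–6.1% |
| 5% | 5.6–7.6% | 6.9–11% |
| 10% | 7.7–13.6% | 11–25% |

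If non-completers do as well as completers, every entry is 4.0%.

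**Step 4: how far the completion record reaches.** With 0 of 32 failing to complete, the one-sided 95% upper bound is 1 − 0.05^(1/32) = 8.9%. The 5% row is compatible with that; the 10% row lies just outside it.

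**Step 5: power.** With 57 completers per cohort the stated powers become 87.1% (A) and 89.1% (B); with 54, 85.5% and 87.6%. Analysing all 60 who start keeps 89% and 90%.

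**The case against.** The strongest reply is that the loss may never occur. The course is five days, two weeks at most. Patients enter with Karnofsky status of at least 70 and life expectancy above three months, and the only completion figure for this kind of schedule is 32 of 32. Part of cohort B, patients given chemotherapy alone for unresectable disease and then 6.6 Gy x 5, closely resembles that earlier trial. Follow-up imaging starts at 4–6 weeks, so what is lost is death or decline during treatment plus the later outcomes of those who stop, not early progression in general. All of this stands, and it limits the size. It does not settle the matter for cohort A, which is re-irradiated and has no completion figure, or for courses spread over two weeks, since the earlier trial used consecutive days.

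Second, LPFS is secondary. The one-sided 0.04 test appears only in the sample-size section; section 13.6 plans a Kaplan-Meier estimate with a 95% confidence interval and names no final LPFS test. This also stands. A reader might infer that the trial's type I error is inflated to 11% or 25%. The documents do not support that: those figures are the extreme for cohort B, they concern the test used for LPFS power, and the primary endpoint is late gastrointestinal toxicity, which section 13.2 does not restrict.

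Third, a reader might want the same all-treated rule for toxicity. No defect is shown there, and the change could do harm. A patient who dies before three months cannot have late toxicity but would count in the 60 for the rule of 16 or fewer events. If 5% or 10% of patients contribute no events and the rest have a 40% rate, the overall rate is 38% or 36%, and the exact two-stage type I error rises from 2.1% to 4.2% or 7.9%.

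**Conclusion.** The point holds as a conditional one. Section 13.2 selects on a post-baseline event, and nothing elsewhere in the plan repairs it. A reader might go further and say that LPFS in this trial is biased upward. The documents do not show that: the bias needs patients who start and do not finish, and who fare worse than completers, and no rate for either is given.

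At an assumed 5% non-completion, the upward shift at the null is 0.8–1.6 percentage points in A and 1.3–2.6 in B, and a nominal 4% test rejects about 5.6–7.6% and 6.9–11% of the time. The ranges run from non-completers having half the average LPFS to all of them failing by one year, and rest on the exponential model of section 13.4.2. With full completion or non-informative stopping there is no effect. The point is worth correcting because LPFS is powered against fixed nulls and feeds the efficacy stop, and because the population can be settled in advance with one sentence.

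**What to change.** Replace the sentence in section 13.2 with:

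*Efficacy analyses include all patients who receive at least one fraction of SBRT, from the SBRT start date; an analysis of patients who complete all five fractions is a sensitivity analysis.*

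Report the number of non-completers in each cohort. State that they stay on the scheduled progression follow-up: section 6.5 promises only survival information for patients who are removed or discontinue, and LPFS needs progression dates. Leave the toxicity population out of this change.

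The cost is a possibly slightly lower LPFS estimate and progression follow-up for what should be a few patients. The stated power on 60 per cohort is kept.
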